7.5 Pharmacokinetic Assessments

On the schedule shown in [Table 2](#) and [Table 3](#), blood samples (6 mL) for Part A (adult subjects) and 4 mL for Part B (pediatric subjects) will be collected in sodium fluoride and potassium oxalate (NaFKO) anticoagulant for analysis of tazarotene and tazarotenic acid plasma concentrations. If vital sign measurements and PK blood samples are scheduled at the same time, the PK blood samples are to be collected before blood pressure and heart rate are recorded. At each specified time, 2 aliquots of plasma will be prepared and stored until the part of the study is completed and will then be sent to designated analytical laboratory (Algorithme) for analysis.

The PK assessment for Part A has been conducted prior to Part B. Based on the full PK profile of Test and Reference treatments in Part A, the sparse sampling schedule for pediatric subjects in Part B has been decided.

The procedures for blood sample collection, plasma separation, storage and sample shipment to each clinical site will be described in a sample processing instruction supplied by the bioanalytical facility.

Tazarotene and tazarotenic acid plasma concentrations will be determined at a designated laboratory from the blinded samples using a validated bioanalytical method.

7.6 Safety Assessments

Safety assessments include visual inspection of the skin (erythema, scaling [peeling]) prior to dose application, assessment of application site reactions (dryness, non-lesional erythema, peeling, stinging, burning, and itching) after dose application, clinical safety laboratory evaluations (chemistry, hematology, and urinalysis), and physical examinations including vital signs (blood pressure and pulse rate). A 12-lead ECG will be performed at the Screening Visit, Baseline visit (Day 1) and Day 21. For females of childbearing potential serum pregnancy tests will be conducted at the Screening Visit and urine pregnancy tests will be conducted at Day 1, Day 7, Day 14 and Day 21. Adverse events will be collected by spontaneous reports from subjects, by directed questioning of subjects, and by observation (see Section 8 for details about AEs). Adverse events, whether believed by the investigator to be related or unrelated to treatment, will be recorded on the CRF.

Before each dose application, the investigator or designated trained site staff will visually inspect the skin and grade erythema and scaling using the scales shown in [Table 6](#) and [Table 7](#), respectively.

After each dose application, the investigator or designated trained site staff will assess application site reactions by examining treated areas for clinically significant non-lesional erythema, peeling, and dryness that will be graded as shown below ([Table 6](#), [Table 7](#), [Table 8](#)) and recorded on the CRF. Assessments will be recorded separately for the face and (if applicable) neck, chest and/or back (including shoulders). The investigator or designated trained site staff will also ask the subject if any stinging ([Table 9](#)), burning ([Table 10](#)), or itching ([Table 11](#)) has occurred on the face (neck, chest and/or back (including shoulders), if applicable since the previous drug application. Day 1 assessments are made prior to first application. An AE should be recorded if the severity is worse than at Day 1. In addition, overall cutaneous tolerance should be graded at Day 21, or the last visit if earlier, using the grading shown in [Table 12](#). The local cutaneous tolerance signs and symptoms will be assessed separately for the

face and neck, chest and/or back (including shoulders) using the same scales below and should be performed within 1 hour of dose application.

Table 6: Scoring of Non-Lesional Erythema

Severity	Score	Description
None	0	No erythema
Mild	1	Light pinkness present
Moderate	2	Definite redness, easily recognized
Severe	3	Intense redness

Table 7: Scoring of Peeling/Scaling

Severity	Score	Description
None	0	No peeling
Mild	1	Barely perceptible shedding, noticeable only on light scratching or rubbing
Moderate	2	Obvious but not profuse shedding
Severe	3	Heavy scale production

Table 8: Scoring of Dryness

Severity	Score	Description
None	0	No dryness
Mild	1	Slight barely perceptible fine superficial scale
Moderate	2	Clearly perceptible fine scale giving skin a powdery appearance
Severe	3	Marked roughness, cracked skin with fissures

Table 9: Scoring of Stinging

Severity	Score	Description
None	0	No stinging
Mild	1	Slight sharp, tingling/stinging sensation; not really bothersome
Moderate	2	Definite sharp, tingling/stinging sensation; that is somewhat bothersome
Severe	3	Sharp, tingling/stinging sensation that has caused definite discomfort

Table 10: Scoring of Burning

Severity	Score	Description
None	0	No burning
Mild	1	Slight warm, burning sensation; not really bothersome
Moderate	2	Definite warm, burning sensation; that is somewhat bothersome
Severe	3	Hot, burning sensation that has caused definite discomfort

Table 11: Scoring of Itching

Severity	Score	Description
None	0	No itching
Mild	1	Slight itching; not really bothersome
Moderate	2	Definite itching that is somewhat bothersome, without loss of sleep
Severe	3	Intense itching that has caused pronounced discomfort; night rest interrupted and excoriation of the skin from scratching may be present

Table 12: Overall Tolerance

Grades	Score	Description
Excellent	0	No signs of irritation during the study
Good	1	Slight signs of irritation during the study, which resolved by the end of the study
Fair	2	Signs of irritation throughout the study
Poor	3	Subject discontinued due to irritation
Irritation is defined as any sign or symptom of intolerance.		

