7. Sitting blood pressure, pulse rate at pre-dose and at 1 and 8 hours after evening dose application with an allowable window of \pm 15 minutes on Day 14 and Day 21. On non-confinement days, sitting vital sign measurements will be done pre-evening dose (within 15 minutes of dosing) and within 1 hour after evening dose application.
8. Blood sampling for pharmacokinetics will be done at pre-specified time points (for Part A) and sparse sampling for Part B, as described in [Table 2](#) and [Table 3](#), respectively. Allowable sampling window is \pm 15 minutes for each timepoint.
9. Disease severity assessment will be performed by Investigator's Global Assessment (IGA) score and lesion counts at baseline and at PK Sampling days.
10. Before each dose application, the investigator or designated trained site staff will visually inspect the skin and grade erythema and scaling/peeling. After each dose application (within 1 hour of dosing), the investigator or designated trained site staff will assess application site reactions of non-lesional erythema, peeling, dryness and ask the subject if any stinging, burning, or itching has occurred.

11. Adverse events will be collected from signing of the Informed Consent at Screening through end of the study and any adverse events spontaneously reported by subjects for a period of 30 days following the last blood sample of the study.

Table 2: Schedule of Blood Sample Collection for Pharmacokinetic Analysis

Day	Part A (Adults: 17 years or older)		Part B (Pediatrics)	
	Test Treatment	Reference Treatment	Test Treatment (9 years to 16 years 11 months)	Reference Treatment (12 years to 16 years 11 months)
1	Prior to evening dose	Prior to evening dose	Prior to evening dose	Prior to evening dose
12	Prior to evening dose	Prior to evening dose		
13	Prior to evening dose	Prior to evening dose		
14-15	Prior to evening dose and serial sampling at 1, 2, 4, 6, 8, 12, 14, 16, 18, and 24 hours post 1st evening dose application.	Prior to evening dose and serial samples at 1, 2, 4, 6, 8, 12, 14, 16, 18 and 24 hours post dose application.	Sparse ¹ samples) as per sampling design in Table 3	Sparse ¹ samples as per sampling design in Table 3 .
19	Prior to evening dose	Prior to evening dose		
20	Prior to evening dose	Prior to evening dose		

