6.2 Treatment Regimen

For all dosing days (except confinement days), subjects will come to the clinical site ± 1 hour of each dose application (e.g., around 7:00 pm and 7:00 am) for twice-daily application of Test product and (e.g. around 7:00 pm) for once-daily application of Reference product. Subjects will leave the clinical site after completion of the scheduled activities. On Day 1, subjects will come to the clinical site prior to the evening dose application (the first study treatment) and on Day 14 and Day 21 subjects will come to the clinical site before scheduled dosing allowing sufficient time for all pre-dosing assessments to be performed. The daily application time should be set based on the time of Day 1 application and should be followed for all applications through Day 22.

For each treatment arm, approximately 5 grams of Test or Reference product will be applied by the subject to the face, neck, and upper chest and will be applied by a member of the clinical staff to the shoulders and upper back (with the total area not exceeding 15% of the body surface area) over 21 consecutive days (Days 1 to 21). The study product should be applied to all affected areas [face, neck, upper chest, and/or upper back (including shoulders)] avoiding contact with the eyes, eyelids, and mouth. Subjects will be asked to refrain from applying emollients (moisturizers, creams) to the application areas at least an hour before dose application.

Note: For age group 9-11 years 11 months, approximately 4 grams of test product will be applied considering their lesser BSA.

The following steps should be taken to ensure consistent product application across time points and subjects:

1. Weigh the empty boat and record weight (e.g. 2.38g)
2. Dispense 5g of product into the boat and record total weight (e.g. 7.38g) [For age group 9-11 years 11 months, dispense 4g of test product into the boat and record total weight (e.g. 6.38g)]
3. Dose the subject
4. Put the empty boat on the scale and record the final weight (e.g. 2.41g)
5. Subtract the full boat weigh from the final weight to get the total weight of product applied ($7.38-2.41 = 4.97\text{g}$) [For age group 9-11 years 11 months, subtract the full boat weight from the final weight to get the total weight of product applied (e.g. $6.38-2.41 = 3.97\text{g}$)]

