Study staff should wear gloves at all times while handling or applying the study product. If powdered gloves are worn, they should be rinsed and dried prior to handling study product.

Test Product

The Test product will be applied twice daily, 12 hours apart (± 1 hour) (morning and evening), for 21 days (42 consecutive doses). Before each dose application, subjects will take a brief warm shower to wet their skin. Approximately 5 grams of the product will be applied by the subject to the face, neck, and upper chest and will be applied by a member of the clinical staff to the shoulders and upper back, and rubbed into the skin until foamy (approximately 30 seconds for the total application area). After being left on for about 1 minute, the subject will rinse off the Test product in the shower for about 1 minute. On Day 22, the last dose application in morning will not be rinsed off in the shower; however, the subject will be permitted to towel dry after the Test product has been on for approximately one minute. Twelve hours following the last application,, the subject will rinse off in the shower for 1 minute. The subject should bare their exposed body parts when the product is rinsed off and the clinical staff should ensure that no residues are left on the body.

Note: For age group 9-11 years 11 months, approximately 4 grams of test product will be applied considering their lesser BSA.

Reference Product

The Reference product will be applied to dry skin once daily in the evening for 21 consecutive days. There should be a 24 hour interval between applications (± 1 hour). Approximately 5 grams of the product will be applied by the subject to the face, neck, and upper chest and by a

member of the clinical staff to the shoulders and upper back. The applied cream will be left on for 12 hours and showering will not be permitted until at least 12 hours after the application.

All Subjects

The times of dose applications should be recorded on the case report form (CRF).

Heavy make-up used to cover-up blemishes and sunscreen should be removed before study product application using a gentle cleanser approved by the investigator, such as Cetaphil Gentle Skin Cleanser, etc.

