6. On Day 15, prior to the evening dose application for Test and Reference products, assess severity of acne by IGA scoring and measurement of lesion count. IGA scoring will be done prior to lesion count.
7. Prior to each dose application, visually inspect the skin and record erythema and scaling (peeling) grades.
8. Apply assigned study product (morning and evening applications for subjects assigned to the Test product, evening application for subjects assigned to Reference product).
9. After each dose application, perform local cutaneous safety evaluation for dryness, non-lesional erythema, and peeling within 1 hour of dosing. The investigator or designated trained site staff should also ask the subject if any burning, stinging, or itching has occurred on the face since the last application. These evaluations should be recorded separately for the face and, if applicable, chest/back (including shoulders).
10. Collect AE data.
11. Update concomitant medications data.
12. Subjects will leave the clinical site after completion of the clinical activities except as noted below for Days 14 to 15.
13. On Day 14 subjects will be housed at the clinical site from prior to the evening dose application, allowing sufficient time for all pre-dosing assessments to be performed, until after the 24-hour PK sample has been collected on Day 15. The morning dose application for Test treatment will be performed on the morning of Day 15. The 24-hour PK sample collection will be followed by the Day 15 evening dose application for Test and Reference product.
14. On Days 14 to 15, PK blood sample collection will occur at the following times:
In Part A (adult subjects, age 17 years or older), blood samples will be collected prior (pre-dose) to the Day 14 evening dose application for Test and Reference treatments and at 1, 2, 4, 6, 8, 12, 14, 16, 18, and 24 hours post dose application.
15. In Part B for Test treatment (subjects age 9 years to 16 years 11 months) and Reference treatment (subjects 12 years to 16 years 11 months), a maximum of 4 blood samples will be collected as per the sparse sample design ([Table 3](#)) Complete the CRF.

7.10.4 Days 21 and 22

Subjects will be confined to clinic prior to evening dose application of Test or Reference treatment, allowing sufficient time for all pre-dosing assessments to be performed on Day 21 until [the completion of clinical activities per schedule](#) on Day 22.

1. On Day 21, perform physical examination.

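### No on-treatment dryness grade is taken before a dose: dryness is scored within 1 hour after application, on cream-covered Reference skin and freshly rinsed Test skin, so the score may miss dryness and may do so differently by arm.

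*Combined protocol and SAP*

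**What the plan says.** **Before dosing.** Section 7.6: "Before each dose application, the investigator or designated trained site staff will visually inspect the skin and grade erythema and scaling". Table 1 footnote 10, 7.10.2 item 12, 7.10.3 item 7 and 7.10.4 item 6 name the same two signs.

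**After dosing.** Section 7.6 has staff "examining treated areas for clinically significant non-lesional erythema, peeling, and dryness that will be graded as shown below". Sections 7.10.3 (item 9) and 7.10.4 (item 8) give the timing: "After each dose application, perform local cutaneous safety evaluation for dryness, non-lesional erythema, and peeling within 1 hour of dosing". Table 1 footnote 10 agrees: "After each dose application (within 1 hour of dosing), the investigator or designated trained site staff will assess application site reactions".

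**State of the skin at that time (6.2).** For Reference: "The applied cream will be left on for 12 hours and showering will not be permitted until at least 12 hours after the application". Test subjects shower before application, rub the lotion to a foam, leave it for about a minute and rinse it off in the shower. The Day 22 morning Test dose is the exception, because it is left on.

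**The scale.** Table 8 grade 1 rests on faint superficial scale. Grade 2 reads "Clearly perceptible fine scale giving skin a powdery appearance".

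**Use of the score.** Section 11.5.2 tabulates dryness by treatment group and visit, and repeats the table without subjects who had signs or symptoms at Baseline. Section 7.6 requires an adverse event to be recorded when severity exceeds that of Day 1.

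**The concern.** Dryness is part of secondary objective (b), safety and tolerability of each treatment, and Section 8 names dry skin among the commonest reactions to the cream (10% to 30% of subjects). A grade that depends on seeing fine scale could be affected by a film of cream or by recent wetting. The two arms are in different states when graded: one leave-on, one washed. A difference between the arms in the 11.5.2 table could therefore reflect the condition of the skin at grading as well as the product. No analysis can later supply a pre-dose grade that was never taken.

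**Working it through.** The plan states no sample-size or power figure that bears on this, so the check is a count of applications and a comparison of sections.

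**1. Number of applications (6.2, 7.10).**
- Test: evenings of Days 1 to 21 (21) + mornings of Days 2 to 22 (21) = 42, which reproduces the plan's 42.
- Reference: evenings of Days 1 to 21 = 21, which reproduces the plan's 21.

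**2. State of the skin at each post-dose dryness grade, assuming one grade per application.**

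| Day 1 reading | Test, post-dose | of which rinsed | of which unrinsed | Reference, post-dose, cream on |
|---|---|---|---|---|
| Day 1 graded after first dose (7.10.2 item 16) | 42 | 42 − 1 = 41 | 1 (Day 22 morning) | 21 |
| Day 1 graded before first dose (7.6) | 42 − 1 = 41 | 41 − 1 = 40 | 1 (Day 22 morning) | 21 − 1 = 20 |

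Under either reading, the number of on-treatment dryness grades scheduled before a dose is 0 in both arms.

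**3. The Day 1 conflict.** Section 7.6 places the Day 1 assessments before the first application. In 7.10.2 the dryness evaluation is item 16, after the first dose (item 14) and after the post-dose vital signs (item 15). Table 1 footnote 10 also places it after dosing. If 7.6 governs, the Day 1 grade is taken before any product and every later grade after it. The adverse event rule then compares grades taken under unlike conditions, and so does the 11.5.2 table that leaves out subjects with baseline signs.

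**4. Dryness against the other signs.** Erythema and scaling are graded both before and after each dose. Stinging, burning and itching are asked about for the whole time since the previous application. Dryness alone has neither a pre-dose grade nor a question covering the interval. Yet just before dosing there is a period largely free of other products: subjects are asked to "refrain from applying emollients (moisturizers, creams) to the application areas at least an hour before dose application".

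**5. Scale of the summary.** Planned Reference enrolment is 12 (Part A) + 12 (Part B) = 24. Each Reference subject whose dryness went unseen would lower the Reference percentage by 1/24 = 4.2 percentage points. The documents give no basis for saying how many subjects, if any, this would be.

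**The case against.** **Safeguards exist.** Scaling is graded before every dose on Table 7, whose mild grade is close in wording to Table 8 grade 1. Section 8 asks investigators to watch for clinically significant dryness at every visit and to report worsening from Baseline as an adverse event, without confining this to the hour after dosing. Adverse events also come from spontaneous reports and questioning, and Table 12 records overall tolerance. This stands: a reader might infer that dryness adverse events depend only on the post-dose score, and they do not. But none of these safeguards gives a dryness grade on skin free of just-applied product, and 11.5.2 reports dryness separately from peeling.

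**Masking is an inference.** The documents hold no data on whether cream or washing hides fine scale. The emollient restriction concerns what subjects apply beforehand and says nothing about the effect of the Reference cream. A reader might infer that dryness is understated on Reference and so biased against Test. That is not supported, because washing could also alter the Test score, and neither size nor net direction can be derived.

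**The stakes are modest.** The objective concerns each treatment, safety is summarised descriptively, and Section 11.1 says powering is not required. Different skin states are inherent in comparing a wash-off with a leave-on product. This is fair, and it limits the weight of the point. It does not explain why dryness is missing from an inspection that already takes place.

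**A pre-dose grade is not fully comparable either.** It falls about 12 hours after the last application for Test and about 24 hours for Reference, and moisturiser with SPF is allowed daily. Both limits stand and should be stated with the results.

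**Conclusion.** The point holds as a gap in a descriptive secondary assessment. No on-treatment dryness grade is scheduled before a dose. The grades that are scheduled come within an hour of application, under conditions that differ by arm. They may miss dryness at grades 1 and 2 and may do so unequally; this assumes that a cream film or recent wetting can obscure fine scale, which is plausible but not shown in the documents.

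A reader might go further and say that every dryness score in the study is post-dose. That cannot be asserted, because 7.6 puts the Day 1 grade before the first application. The post-dose counts are 42 and 21 or 41 and 20 (Test and Reference), depending on which section governs. Nor is every Test grade on rinsed skin, given Day 22. The conflict between 7.6 and 7.10.2 over Day 1 is a defect in itself and must be reconciled. The primary pharmacokinetic objective is not touched.

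**What to change.** 1. Add dryness (Table 8) to the pre-dose grading in 7.6, Table 1 footnote 10, 7.10.2 item 12, 7.10.3 item 7 and 7.10.4 item 6. State that it is done before the Test pre-application shower and after any make-up or sunscreen has been removed. At present the documents do not say whether the Test inspection precedes the shower.
2. Reconcile 7.6 with 7.10.2 item 16 and Table 1 footnote 10 on the Day 1 timing. Take a pre-dose dryness grade on Day 1 as well, so that the comparison with Day 1 uses grades taken under like conditions.
3. In 11.5.2, report pre-dose and within-1-hour dryness scores as separate summaries by treatment and visit. Keep the post-dose summary for all subjects.
4. State beside the pre-dose summary that the time since the last application is about 12 hours for Test and about 24 hours for Reference.

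**Cost.** One more score at an existing inspection, one CRF field and a short addition to the analysis text. The 24 adults planned for Part A, which the protocol describes as already conducted, will have post-dose dryness scores only. The pre-dose summary will therefore cover Part B subjects dosed after the change.

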Approximately 62 subjects will be randomized to receive either Test or Reference product, stratified by age (Adult subjects: 17 years or older; Pediatric subjects: 9 years to 16 years 11 months for the Test product and 12 years to 16 years 11 months for the Reference product) with approximately even distribution between males- and females in each age-strata. The study will be conducted in two parts, Part A and Part B in a sequential manner. Based on full PK profiles generated for adult subjects in Part A, the sparse PK sampling design in pediatric population has been established in Part B.

Part B (age 9 years to 16 years 11 months for DFD-03 Lotion arm and age 12 years to 16 years 11 months for Tazorac Cream arm) will enroll up to 38 subjects, which will include at least 6 subjects 9 to 11 years of age, and among those at least 2 subjects between 9 and 10 years of age. Target enrollment is 32 subjects, but up to 6 additional subjects may be enrolled to reach a minimum of 16 evaluable subjects, who have sparse samples collected on Day 14 and Day 21, randomized to the Test treatment.

PK profiling will be performed on Day 14 and on Day 21. Day 14 is selected as the earliest time point at which the steady state is expected to be achieved in subjects with moderate acne vulgaris, before any significant improvement in skin barrier occurs.

In Part A, 24 adult subjects will be enrolled such that 12 subjects each will be assigned to receive either Test or Reference treatment. In Part B, up to 38 subjects will be enrolled where approximately 26 subjects will receive Test treatment and 12 subjects will receive Reference treatment. Enrollment will continue until at least 16 evaluable subjects randomized to the Test treatment in Part B complete the study.

For 21 days, study product will be applied on the face, neck, upper chest, shoulders and upper back region, not exceeding 15% of the body surface area. The Test product will be applied twice daily, 12 hours apart (morning and evening; 42 consecutive doses) and the Reference product will be applied once daily in the evening (21 consecutive doses).

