 11. Randomize subject.
 12. Prior to first evening dose, visually inspect the skin and grade erythema, scaling/peeling.
 13. Collect pre-dose pK blood sample.
 14. Administer first dose.
 15. After administering first dose, collect sitting vital signs within 1 hour post-dose.
 16. Perform local cutaneous safety evaluation for dryness, non-lesional erythema, and peeling. The investigator or designated trained site staff should also ask the subject if any burning, stinging, or itching has occurred. These evaluations should be recorded separately for the face and, if applicable, neck, chest and/or back (including shoulders).
 17. Complete the CRF for randomized subjects.

7.10.3 Daily, Day 2 Through Day 20

Subjects will come to the clinical site ± 1 hour of each dose application (except Day 14). Subjects assigned to Test product will come to the clinical site for evening and morning twice-daily application and subjects assigned to Reference product will come to the clinical site for evening application. Subjects will leave clinic after completion of clinical activities for each dose application.

Subjects will be confined to the clinic from prior to evening dose application of Test or Reference on Day 14, allowing sufficient time for all pre-dosing assessments to be performed, until after the 24-hour PK sample collection and evening dose application on Day 15.

1. On Day 7 and Day 14, prior to evening dose application, perform urine pregnancy test for female subjects, urine drug screen and alcohol breath test. Any subject with a positive alcohol breath test and/or positive drug screen should be discontinued from the study.
2. Alcohol breath test will be additionally performed on Days 12, 13, 19 and 20. Any subject with a positive alcohol breath test and/or positive drug screen should be discontinued from

the study.

3. On Day 14, collect sitting vital signs (blood pressure and pulse) pre-evening dose and at 1, and 8 hours after evening dose application for Test and Reference product.
4. On non-confinement days (Days 2-13 and Days 15-20), collect sitting vital signs (blood pressure and pulse) pre-evening dose (within 15 minutes of dosing) and within 1 hour after evening dose application for Test and Reference.
5. On Days 12 and 13 (steady state), collect PK blood sample. Additionally trough samples will be collected at Day 19 and Day 20. For the pediatric population in Part B, trough samples will not be collected on days 12, 13, 19 and 20.

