11.5.2 Local Cutaneous Safety Evaluation

Non-lesional erythema, peeling, dryness, burning, stinging, and itching scores will be summarized by treatment group and visit including sample size, frequency count and percentage for each visit. A similar summary will be provided excluding subjects with signs or symptoms present at Baseline.

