11.5.3 Adverse Events

All AEs occurring during the study will be recorded and classified on the basis of Medical Dictionary for Regulatory Activities (MedDRA) terminology. Treatment-emergent adverse events (TEAEs) are AEs with an onset on or after the date of the first study product administration. For the safety population, all reported TEAEs will be summarized by treatment group, the number and percent of subjects reporting events, system organ class (SOC), preferred term (PT), severity, relationship to study product, and seriousness. When summarizing TEAEs

by causality and severity, each subject will be counted only once within a system organ class or a preferred term by using the event with the greatest relationship and highest severity within each classification.

Additionally, treatment-related TEAEs will be summarized for each treatment group by SOC and PT, and further by severity. A TEAE will be considered treatment-related if it is reported as possibly, probably, or definitely related to study treatment.

SAEs will be listed by subject. In addition, a list of subjects who prematurely discontinued from the study due to an AE will be provided.

All information pertaining to AEs noted during the study will be listed by subject, detailing verbatim term given by the investigator, preferred term, system organ class, onset date, resolution date, maximum severity, seriousness, action taken regarding study product, corrective treatment, outcome, and drug relatedness. The event onset will also be shown relative (in number of days) to date of first administration.

AEs related to study procedures done before study product administration will be provided in a data listing.

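### More frequent skin grading in the Test arm can raise its subject-level TEAE percentages for transient local signs, and no planned table matches the assessments between arms

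*Combined protocol and SAP*

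**What the plan says.** The synopsis and Section 4 set the regimens. One arm is dosed as follows: "The Test product will be applied twice daily, 12 hours apart (morning and evening; 42 consecutive doses"). Dosing in the other arm is half as frequent: "the Reference product will be applied once daily in the evening (21 consecutive doses"). Under Section 7.10.3, "subjects assigned to Reference product will come to the clinical site for evening application", with no morning visit.

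Grading is tied to dosing. Section 7.6 states: "Before each dose application, the investigator or designated trained site staff will visually inspect the skin and grade erythema and scaling". Table 1, footnote 10, continues: "After each dose application (within 1 hour of dosing), the investigator or designated trained site staff will assess application site reactions". The post-dose assessment covers erythema, peeling and dryness, and the subject is asked about stinging, burning and itching. The AE rule in Section 7.6 is: "An AE should be recorded if the severity is worse than at Day 1".

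Two summaries use these data. Section 11.5.2 says that the local "scores will be summarized by treatment group and visit including sample size, frequency count and percentage for each visit". Section 11.5.3 says that "all reported TEAEs will be summarized by treatment group, the number and percent of subjects reporting events". Table 12 adds an overall tolerance grade at Day 21 or the last visit; its best category requires that no irritation was seen at any time in the study. No text aligns the assessment times of the two arms, and none says what a visit is when Test has two grading occasions in one day.

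**The concern.** The percent of subjects with at least one event depends on how often anyone looks. Counting a subject once per term, as Section 11.5.3 does in its causality and severity summaries, stops repeat counting. It does not remove the higher chance of being caught at least once. Reference cream stays on for 12 hours (Section 6.2), yet no Reference grading is scheduled between about 1 hour after the evening dose and the next evening. Test skin is graded about every 12 hours. A sign that comes and goes within that gap can be recorded in Test and missed in Reference.

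Secondary objective (b) is the safety and tolerability of each treatment. Side-by-side percentages for irritation terms will be read across arms. Part of any excess in Test could be inspection frequency, and a real tolerability advantage of the rinse-off product could be hidden.

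**Working it through.** **Occasions.** Reference: evenings of Days 1 to 21 = 21. Test: the same 21 evenings plus mornings of Days 2 to 22 = 21 + 21 = 42. Both reproduce the plan's dose counts.

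**Looks after the pre-dose baseline on Day 1.** For erythema and peeling, which are graded before and after dosing: Test 42 + 41 = 83, Reference 21 + 20 = 41, ratio 83/41 = 2.02. For dryness, graded only after dosing: 42 against 21.

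**Detection by duration of the sign.** Assumptions, not in the documents: a sign lasts D hours, its onset is spread evenly over the day, and gradings take place just before and up to 1 h after each dose. For erythema and peeling, the chance of seeing an episode is min(1, (D+1)/24) in Reference and min(1, (D+1)/12) in Test. For dryness it is min(1, D/24) and min(1, D/12).

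| D (h) | Erythema, peeling: Reference | Test | Ratio | Dryness: ratio |
|---|---|---|---|---|
| 6 | 0.292 | 0.583 | 2.0 | 2.0 |
| 11 | 0.500 | 1 | 2.0 | 2.0 |
| 12 | 0.542 | 1 | 1.85 | 2.0 |
| 18 | 0.792 | 1 | 1.26 | 1.33 |
| 23 | 1 | 1 | 1.00 | 1.04 |
| 24 | 1 | 1 | 1.00 | 1.00 |

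**Subject level, upper end.** Assume equal and independent risk at each dose occasion, and let P be the Reference percentage over 21 occasions. The risk per occasion is q = 1 − (1−P)^(1/21), so the Test percentage is 1 − (1−q)^42 = 1 − (1−P)². Section 8 gives 10% to 30% for the most common reactions to the 0.1% cream; that range is used for P as an illustration. Planned Test subjects: 12 + 26 = 38.

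| Reference | Test | Ratio | Expected Test subjects (of 38), against the count at the Reference rate |
|---|---|---|---|
| 10% | 19.0% | 1.90 | 7.2 against 3.8 |
| 20% | 36.0% | 1.80 | 13.7 against 7.6 |
| 30% | 51.0% | 1.70 | 19.4 against 11.4 |

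**What this does not show.** The second model cannot separate detection from effect. If each application truly caused a reaction with probability 1% and every reaction were seen, 1 − 0.99^42 = 34.4% and 1 − 0.99^21 = 19.0%. The same gap would then be wholly real.

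**Symptoms.** Section 7.6 asks about the time since the previous application: about 12 h per question in Test and about 24 h in Reference. With full recall both arms are covered almost continuously, so the ratio is about 1.

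**After matching.** Restricted to evening gradings on Days 1 to 21, each arm has 21 occasions and 41 looks. The ratio of looks is 1.00, and under the independence model a 10% Reference rate gives 10% in Test.

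**The case against.** A reader might infer that a planned comparison of safety between arms is biased. The documents do not support that. The objective concerns each treatment, Section 11.4 limits safety to descriptive statistics, and no safety test or margin is set. What remains is how the adjacent percentages will be read.

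A reader might also infer that every score above Day 1 becomes an AE. Sections 7.6 and 8 direct attention to clinically significant erythema, peeling and dryness, and Section 8.2 lets intermittent AEs be recorded once. This narrows the mechanism without removing it: the pre-dose gradings and the trigger sentence carry no such threshold.

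It is tempting to call the Section 11.5.2 tables inflated as well. A percentage at one visit does not rise with the number of visits. It would do so only if the two Test occasions in a day were merged into a worst score, which the plan neither states nor rules out.

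Finally, long-lasting signs would be seen in both arms, spontaneous reports may recover some missed Reference reactions, and Test skin receives twice as many applications, so some excess may be real. All of this stands. It limits the size of the effect and is a reason to show a matched table beside the planned ones, not to discard the planned ones.

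**Conclusion.** The point holds for the subject-level TEAE percentages in Section 11.5.3 and the cumulative grade in Table 12, and only for transient erythema, peeling or dryness. Detection of an episode is doubled in Test for signs lasting up to about 11 h and equal in the two arms from about 24 h. At subject level, where episodes can recur, inflation therefore runs from none to just under twofold. These figures rest on assumed durations, evenly spread onset and, for the upper end, independence between occasions; correlation within subjects reduces the gap.

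For stinging, burning and itching the effect is small, provided the question is taken to reach back to the preceding dose. It is asked after dosing, so sites could read it as covering only the last hour. The doubling describes the number of looks and is not an estimate of the bias. The plan as written cannot divide an excess in Test between closer inspection and twice-daily use.

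**What to change.** Keep all planned TEAE tables and make these additions in Sections 11.5.2 and 11.5.3, or in the separate SAP that Section 11 promises before database lock:

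- **Section 11.5.2:** define a visit as one grading occasion. Tabulate Test morning and evening gradings separately, not as a merged worst-of-day score.
- **Section 11.5.3:** add one supplementary table, derived from the scores on the CRF, of the percent of subjects in each arm with worsening from Day 1 in erythema, peeling and dryness at any evening grading on Days 1 to 21. Show Test morning gradings separately, including those around the unrinsed Day 22 dose.
- **Symptoms:** do not use evening answers alone, since that would set about 12 h of Test recall against about 24 h of Reference recall. Combine the Test morning and evening answers that cover each 24 h, and state the recall period.
- **Day 1 reference:** Section 7.6 places the Day 1 assessments before the first application, whereas Section 7.10.2 lists dryness and the symptom questions after it. Reconcile these so that worsening has one baseline.
- **Text:** state that the unrestricted local-reaction TEAE percentages, and the Table 12 grade, reflect unequal assessment frequency as well as twice as many applications.

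The cost is one extra table and a few sentences, with no new visit or procedure. The downside is that Test signs seen only in the morning fall outside the matched comparison; the separate morning display keeps them visible.
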